Appendix C: Informed Consent (Template)

Appendix D: Case Report Forms (CRFs)

Protocol Synopsis**Protocol ID 4600**

Sponsor	Torax Medical, Inc. [name] [contact] [contact]
Study Title	RELIEF Study: A Prospective, Multicenter Study of Reflux Management with the LINX® System for Gastroesophageal Reflux Disease after Laparoscopic Sleeve Gastrectomy
Study Device	The LINX® Reflux Management System (LINX)
Indication	The LINX® Reflux Management System is a laparoscopic, fundic-sparing anti-reflux procedure indicated for patients diagnosed with Gastroesophageal Reflux Disease (GERD) as defined by abnormal pH testing, and who are seeking an alternative to continuous acid suppression therapy (i.e. proton pump inhibitors or equivalent) in the management of their GERD.
FDA Approval	March 22, 2012
Study Design	An observational, multicenter, single-arm study with prospective enrollment.
Purpose	To evaluate the safety and efficacy of LINX for its approved indication in patients who have had prior gastric surgery, specifically, laparoscopic sleeve gastrectomy (LSG).
Objective	To confirm safety and efficacy after LSG in patients indicated for LINX is similar to the outcomes that formed the basis for Premarket Approval (PMA) to support modification of the current labeling with a statement that prior gastric surgery with LSG has been evaluated for safety and efficacy.
Number of Subjects	Up to 30 subjects
Study Centers	Up to 12 implanting sites in the U.S.
Study Duration	36 months (24-month enrollment period + 12-month follow-up period)
Evaluation of Safety	Rate of serious device and procedure related adverse events assessed by reporting all adverse events and by estimating the rate of serious device and procedure related adverse events through 12 months post implantation. Safety will also be evaluated by endoscopy to assess the mucosa and abdominal/chest X-ray evaluations to verify device location at 12 months post implantation.
Evaluation of Efficacy	Percentage of subjects reporting at the 12-month follow-up: 
• Normalization of total distal acid exposure (% total time pH<4) or at least 50% reduction in total distal acid exposure compared to baseline• At least 50% reduction in total GERD-HRQL score compared to baseline (off PPIs)• At least 50% reduction in average daily PPI dosage compared to baseline
Study Management	Torax Medical Inc. or Designate

Schedule of Data Collection

Screening/ Baseline	Implant /Discharge	2-week Post-Operative Visit (Day 7 – Day 21)	3 months (Day 76 – Day 104)	6 months (Day 150 – Day 210)	12-month Visit (Day 305 – Day 425)	Data Collected
X						Demographics (gender, race)
X					X	Height and Weight
X					X	Medical History
	X					Implant Procedure and Discharge Data
X					X	Endoscopy (LA Grade Classification)
X					X	Manometry/Motility
X	X ³				X	Barium Esophagram
	X ³				X	Upright Bi-Planar X-Rays (AP and Lateral)
X			X	X	X	GERD Medications
X ¹			X ²	X ²	X ²	GERD-HRQL
X ²			X ²	X ²	X ²	Foregut Symptom Questionnaire
X ²					X ²	Esophageal pH Measurements (off PPIs)
	X	X	X	X	X	Device and/or Procedure Adverse Events

X=All study subjects

¹Screening/baseline GERD-HRQL questionnaire is completed twice: once on GERD medication and once off GERD medications for at least 7 days, with the exception of antacids which can be taken up until the morning of assessment.

² Completed/conducted off GERD medications for at least 7 days, with the exception of antacids which can be taken up until the morning of assessment.

³Testing performed after implant and prior to discharge or within 7 days of implant, whichever occurs first.

1.0 BACKGROUND

There are several types of surgical weight loss procedures. The Laparoscopic Sleeve Gastrectomy (LSG) is a restrictive weight loss procedure that is performed by removing about 75% of stomach. It is estimated that as many as 84.1% of the subjects with pre-existing Gastroesophageal Reflux Disease (GERD) that undergo the LSG can continue to have chronic GERD symptoms¹ and as many as 8.4% of patients that did not have pre-existing GERD can develop new onset GERD symptoms. The traditional surgical method of using the patients' anatomy (fundus) to perform a fundoplication is no longer an option for these patients and the treatment alternatives for patients experiencing GERD symptoms after LSG are few. The Roux-en-Y Gastric bypass (RYGB) has been recommended as a conversion procedure for those who develop or continue to have reflux after LSG. However, the LINX Reflux Management System (LINX) has been considered as an alternative and less invasive option that may potentially have fewer complications compared to RYGB.

2.0 THE LINX REFLUX MANAGEMENT SYSTEM

2.1 DEVICE DESCRIPTION

The LINX® Reflux Management System is a laparoscopic, fundic-sparing anti-reflux procedure indicated for patients diagnosed with Gastroesophageal Reflux Disease (GERD) as defined by abnormal pH testing, and who are seeking an alternative to continuous acid suppression therapy (i.e. proton pump inhibitors or equivalent) in the management of their GERD. The LINX device is a permanent implant placed at the area of the lower esophageal sphincter (LES) and is designed to augment a weak LES and minimize or eliminate GERD-related symptoms.

[figure not shown]
2.2 REGULATORY HISTORY

The LINX System has been evaluated in two IDE studies under G060172. A feasibility study enrolled 44 study subjects at 4 study centers (2 US, 2 OUS), with the first implant performed in February 2007. The pivotal study enrolled 100 study subjects at 14 centers (13 US, 1 OUS), with the first implant in January 2009. A Post Approval-Study of the LINX System is ongoing to supplement existing safety and efficacy data. The LINX Reflux Management System received approval for U.S. marketing from the Food and Drug Administration (FDA) on March 22, 2012.

[figure not shown]
The LINX device consists of a series of titanium beads each with a magnetic core connected together with independent titanium wires to form an annular shape, when implanted (**Figure 1**). The attractive force of the magnetic beads is designed to provide additional strength to keep a weak LES closed. During swallowing, the

¹DuPree et al *JAMA Surg.* 2014;149(4):328-334. doi:10.1001/jamasurg.2013.4323.

magnetic beads slide away from each other on the independent titanium wire “links” to allow esophageal distention as the bolus passes by (**Figure 2**).

The LINX System allows a surgeon, using existing laparoscopic techniques and instruments, to augment a weak sphincter and restore the barrier function of the LES. The mechanism of action for the LINX device is to augment the sphincter’s capacity to resist gastric pressure by using magnetic forces. For abnormal reflux to occur following implantation of the LINX device, gastric pressure must overcome both the native sphincter resistance and the magnetic bond between the LINX beads. Prior to implant, the esophagus is sized to select a device that fits the external diameter of the esophagus. At rest, the LINX device encircles the LES with each bead resting against an adjacent bead, which avoids compression of the esophagus and allows the patient to belch or vomit as necessary. Upon swallowing, the magnetic bond between the beads is overcome by the higher pressures of peristaltic swallowing forces, and the device expands to accommodate a normal swallow (**Figures 3-5**).

LINX device creates resistance with magnetic forces to prevent the LES

Higher pressures from swallowing overcome the magnetic forces,

LINX device does not compress the esophageal wall.

Figure 3: Preventing Reflux

Figure 4: During Swallow

Figure 5: Non-Compressive

3.0 STUDY PURPOSE AND OBJECTIVE

The purpose of this study is to evaluate the safety and efficacy of LINX for its approved indication in patients who have had prior gastric surgery, specifically, LSG. The objective of the study is to confirm safety and efficacy after LSG is similar to the outcomes that formed the basis for Premarket Approval (PMA) in order to support modification of the current labeling with a statement that prior gastric surgery with LSG has been evaluated for safety and efficacy.

4.0 STUDY RATIONALE

The LSG procedure involves removal of the fundus. As a result, fundoplication is extremely difficult to perform with the limited amount of fundus tissue present in patients with prior LSG. Roux-en-Y Gastric bypass (RYGB) has been recommended as a conversion procedure for those who develop or continue to have reflux after LSG. However, LINX has been considered as an alternative and less invasive option that may potentially have fewer complications compared to RYGB. Additionally, patients may not be interested in RYGB due its associated malabsorption. The LINX device is implanted in the area of the gastroesophageal junction (GEJ), which is largely undisturbed with LSG. Patients with prior gastric surgery, such as LSG, have not to date been enrolled in clinical studies for the LINX device. This study is the first to prospectively enroll and evaluate under protocol the LINX device for GERD in post-LSG patients.

5.0 STUDY DESIGN

The study is an observational, multicenter, single-arm study with prospective enrollment. Based on the observational status of the study, No formal statistical hypothesis tests will be conducted. Up to 30 patients meeting the eligibility requirements will be implanted with LINX and followed through 12-months after implant. Up to twelve (12) clinical sites will enroll subjects. The study duration is expected to be about 36 months (24-month enrollment period and 12-month follow-up). Safety evaluations will be ongoing throughout the duration of the study, starting at the implant procedure. Efficacy endpoints will be evaluated at the 12-month visit.

5.1 ASSESSMENT OF SAFETY

Safety will be assessed by evaluating device and/or procedure related adverse events, perioperative complications, device malfunctions, device removals, and hospital readmissions experienced by subjects post-LINX implant out to 12 months. Esophageal anatomy and functionality will be monitored by performing manometry and barium esophagram at 12-months post-implant. This will allow for identification of any abnormal or atypical findings. Further, device migration will be assessed by confirming device position at the GEJ by obtaining upright, bi-plane X-rays and device erosion will be assessed by performing endoscopy at the 12 month visit.

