7.0 STUDY SCHEDULE AND ASSESSMENTS

Table 1 provides a schedule of data collection and follow-up windows. It should be noted that certain data is collected while on and/or off GERD medications.

Standard of care practices for antireflux surgery will be the basis of the assessments performed to determine if a subject is a candidate for the LINX device. Investigators should refer to the LINX Instructions for Use (IFU) for prescribing information (see **Appendix A**). Further, the study center will obtain appropriate study informed consent prior to evaluating the subject study specific evaluations. Data will then be collected at the screening/baseline visit, the implant procedure and the hospitalization period following implant until discharge. The subject will be followed at 2-weeks, 3-months, 6-months, and 12-months post-implant, with data collection occurring at each time point. Follow-up assessments may be completed by telephone or visit, with the exception of the X-rays, manometry, barium swallow, endoscopy and esophageal pH testing which must be conducted during a visit.

Subjects will complete questionnaires to evaluate reflux-related symptoms (GERD-HRQL and Foregut Symptom Questionnaire). With the exception of the GERD-HRQL

at baseline, the questionnaires are completed off GERD medications for at least 7 days, with the exception of antacids which can be taken up until the morning of assessment. At the screening/baseline visit, the questionnaires will be completed twice for the GERD-HRQL – once on GERD medications and once off GERD medications for at least 7 days, with the exception of antacids which can be taken up until the morning of assessment (Table 2).

Table 1: Schedule of Data Collection and Follow-Up Windows

Screening/ Baseline	Implant /Discharge	2-week Post-Operative Visit (Day 7 – Day 21)	3 months (Day 76 – Day 104)	6 months (Day 150 – Day 210)	12-month Visit (Day 305 – Day 425)	Data Collected
X						Demographics (gender, race)
X					X	Height and Weight
X					X	Medical History
	X					Implant Procedure and Discharge Data
X					X	Endoscopy (LA Grade Classification)
X					X	Manometry/Motility
X	X ³				X	Barium Esophagram
	X ³				X	Upright, Bi-Planar X-Rays (AP and Lateral)
X			X	X	X	GERD Medications
X ¹			X ²	X ²	X ²	GERD-HRQL
X ²			X ²	X ²	X ²	Foregut Symptom Questionnaire
X ²					X ²	Esophageal pH Measurements (off PPIs)
	X	X	X	X	X	Device and/or Procedure Adverse Events

X=All study subjects

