¹Screening/baseline GERD-HRQL questionnaire is completed twice: once on GERD medication and once off GERD medications for at least 7 days, with the exception of antacids which can be taken up until the morning of assessment.

² Completed/conducted off GERD medications for at least 7 days, with the exception of antacids which can be taken up until the morning of assessment.

³Testing performed after implant and prior to discharge or within 7 days of implant, whichever occurs first.

Table 2: Completion of Questionnaires and GERD Medication

Visit	GERD-HRQL	Foregut
Baseline/Screening	On GERD medications Off GERD medications	Off GERD medications
3-Month	Off GERD medications	Off GERD medications
6-Month	Off GERD medications	Off GERD medications
12-Month	Off GERD medications	Off GERD medications

The data detailed in **Table 3** will be obtained at each of the identified time points. Use the following guidelines provide suggested methods and documentation for testing (**Appendix B**):

- 4663 Guidelines for Endoscopy testing
- 4664 Guidelines for X-rays testing
- 4665 Guidelines for Barium Esophagram testing
- 4666 Guidelines for Manometry/Motility testing

Table 3: Planned Assessments

Visit	Assessments/Data to be Collected
Screening/ Baseline	
 • Informed Consent • Demographics (Date of Birth, Gender, Race) • Height and weight • GERD History: Duration of PPI use, Years with GERD, GERD New Onset or Pre-existing after LSG • GERD-HRQL (on/off PPIs) and Foregut Symptoms Questionnaire (off PPIs) • Baseline GERD related medication use • Esophageal pH measurements (off PPIs) • Endoscopy • Manometry/Motility • Barium Esophagram • Motivation for surgery • Inclusion/Exclusion criteria evaluation
Implant/ Discharge	
 • Surgery Date • Surgery start and stop time • Implanted device size • Concomitant procedures (e.g. hiatal hernia repair, cholecystectomy) • Barium esophagram and upright Bi-Planar X-Rays (AP and Lateral) • Discharge Date • Perioperative and device and/or procedure related adverse events
2 Week	
 • Device and/or procedure related adverse events
3-Month	
 • GERD-related medication use within the last 30 days • GERD-HRQL (off PPIs) and Foregut Symptoms Questionnaire (off PPIs) • Device and/or procedure related adverse events

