11.9 ADVERSE EVENT REPORTING

If an intraoperative decision is made to not implant the LINX device, the subject will be monitored for procedure related adverse events for a period of at least three months (90 days) or longer if needed until resolution before withdrawing the subject from the study.

If a decision is made to explant the LINX device during the study, the subject will be monitored for explant-related adverse events for a period of at least three months (90 days) or longer if needed until resolution before withdrawing the subject from the study. No other study testing and/or questionnaires would be required after the device is explanted.

For all other subjects starting at the time of implantation and proceeding throughout the duration of the follow-up period, the Investigator will closely monitor each subject for the development of device and/or procedure related adverse events. A subject presenting with new onset dysphagia, abdominal pain, nausea, or vomiting, may be assessed for device migration and/or erosion if symptoms persist and benign causes cannot be established, at the discretion of the Investigator. This may include additional, non-study visit, x-rays or endoscopic evaluation. Adverse events will continue to be monitored at each of the study follow ups until resolution and/or study completion.

For the purposes of this study, a reportable event will be defined as any untoward medical occurrence which has a strong relationship to the LINX device and/or implant procedure and another etiology is unlikely. The Investigator must decide whether each event meets the definition of a Serious Adverse Event (SAE). All device and/or procedure related serious adverse events (SAE) must be reported immediately (within 5 days of discovery) to Torax Medical. SAE reporting to the IRB is per institutional policy.

An AE is considered **serious** if it meets one or more of the following criteria:

- **Is life-threatening or results in death**
Note: The term “life-threatening” in the definition of “serious” refers to an event in which the subject was at risk of death at the time of the event; it does **not** refer to an event that hypothetically might have caused death if it were more severe.
- **Requires subject hospitalization > 24 hours**
- **Requires prolongation of an existing hospitalization**
- **Results in persistent or significant disability/incapacity**
- **Results in fetal distress, fetal death, or a congenital anomaly or birth defect**

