1.2 Study Design

This is an observational, multicenter, single-arm study with prospective enrollment. Based on the observational status of the study, no formal statistical hypothesis tests will be conducted. Up to 30 subjects meeting the eligibility requirements will be implanted with LINX and followed through 12-months after implant. Up to twelve clinical sites will enroll subjects. Safety evaluations will be ongoing throughout the duration of the study, starting at the implant procedure. Efficacy endpoints will be evaluated at the 12-month visit.

Safety will be assessed by evaluating device and/or procedure related adverse events, perioperative complications, device malfunctions, device removals, and hospital readmissions experienced by subjects post-LINX implant out to 12 months. Esophageal anatomy and functionality will be monitored by performing manometry and barium esophagram at 12-months post-implant. This will allow for identification of any abnormal or atypical findings. Further, device migration will be assessed by confirming device position at the gastroesophageal junction (GEJ) by obtaining upright, bi-plane X-rays and device erosion will be assessed by performing endoscopy at the 12-month visit.

Efficacy will be assessed by evaluating the percentage of subjects reporting at the 12-month follow-up:

- Normalization of total distal acid exposure time or at least 50% reduction in total distal acid exposure time compared to baseline.
- >50% reduction in total GERD-HRQL score compared to baseline (off PPIs).
- >50% reduction in average daily PPI dosage compared to baseline.

2 Treatment Assignment

This is a prospective, multicenter, single-arm, observational study, where subjects serve as their own control.

3 Randomization and Blinding Procedures

This is an observational, single-arm study. No randomization will occur, and no blinding procedures will be needed.

4 Interval Windows

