8.6 Safety Analyses

Safety will be assessed by the rate of AEs and SAEs (number and percentage of subjects experiencing). Similar summaries will also be provided for AEs and SAEs related to the study device, as well as for AEs and SAEs related to the study procedures. Related events are those where the event relatedness is indicated as Yes/Probably/Possibly, or Unknown. Esophageal anatomy and functionality will be monitored by performing manometry and barium esophagram at 12-months post-implant. A summary and change from baseline of manometry and motility results will be provided which includes LES length, LES residual pressure, LES intra-abdominal length, LES basal mean pressure, percent peristaltic sequences, distal amplitude, distal contractile integral, percent ineffective swallows, and percent fragmented swallow. Count and percentages will be provided for barium esophagram in the number of subjects who have normal swallow function, number of subjects who have a dilated proximal pouch, number of subjects who have evidence of a hiatal hernia, and if any abnormalities occurred. This will allow for identification of any abnormal or atypical findings. Further, device migration will be assessed by confirming device position at the GEJ by obtaining upright, bi-plane X-rays and device erosion will be assessed by performing an endoscopy at the 12 months visit.

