Appendix: Table Shells and List of Listings to be Generated

Table shells are provided below for all summaries to be generated for this study. These shells are a guide to the general layout of data to be presented. Minor modifications can be made to suit existing programs or macros that are available. Additionally, a list of all listings to be created is provided corresponding to the eCRFs that are used during this study. All fields collected will be listed.

Table 1
Subject Disposition
All Subjects

Characteristics	Total
Signed Informed Consent	xx
Full Analysis Set	xx
Consented Screen Failure	xx
Device not implanted	xx (xx.x%)
Completed the Study [1]	xx (xx.x%)
Withdrawal from the Study [1]	xx (xx.x%)
Reason for Withdrawal [2]	
Withdrawal of consent	xx (xx.x%)
Adverse Event	xx (xx.x%)
Death	xx (xx.x%)
Lost to Follow-up	xx (xx.x%)
Site or Study Termination	xx (xx.x%)
Other	xx (xx.x%)

[1] Percentages are based on the number of subjects who enrolled and implanted as the denominator.

[2] Percentages are based on the number of subjects who discontinued from the study as the denominator.

<Programming note: Only categories observed in the database need to be displayed for Reason for Withdrawal.>

Table 2
 Subject Demographics and Physical Examination
 Full Analysis Set

Characteristic	Total (N = ##)
Age at Consent (years)	
n	xx
Mean (SD)	xx.x (xx.x)
Median (Min, Max)	xx.x (xx, xx)
Gender, n (%)	
Male	xx (xx.x%)
Female	xx (xx.x%)
Ethnicity, n (%)	
Hispanic or Latino	xx (xx.x%)
Not Hispanic or Latino	xx (xx.x%)
Not Reported	xx (xx.x%)
Race, n (%)	
American Indian or Alaska Native	xx (xx.x%)
Asian	xx (xx.x%)
Black or African American	xx (xx.x%)
Native Hawaiian or Other Pacific Islander	xx (xx.x%)
White or Caucasian	xx (xx.x%)
Other	xx (xx.x%)
Height (cm)	
n	xx
Mean (SD)	xx.x (xx.x)
Median (Min, Max)	xx.x (xx, xx)
Weight (kg)	
n	xx
Mean (SD)	xx.x (xx.x)
Median (Min, Max)	xx.x (xx, xx)
Body Mass Index (kg/m ²) at Baseline	
n	xx
Mean (SD)	xx.x (xx.x)
Median (Min, Max)	xx.x (xx, xx)

Denominator and percentages are based on subjects with non-missing data.

<Programming note: Only categories observed in the database need to be displayed for Ethnicity and Race>

Table 3
GERD Medications
Full Analysis Set

Characteristic	Baseline (N = ##)	3 Months Follow-Up (N = ##)	6 Months Follow-Up (N = ##)	12 Months Follow-Up (N = ##)
Currently Taking PPI				
Yes	xx (xx.x%)	xx (xx.x%)	xx (xx.x%)	xx (xx.x%)
No	xx (xx.x%)	xx (xx.x%)	xx (xx.x%)	xx (xx.x%)
PPI Medications				

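### Hospital readmissions and device malfunctions are named safety outcomes, but they are undefined, have no visible collection item, and may be under-counted under the protocol's reporting rule

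*Protocol*

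**What the plan says.** Protocol 5.1 names five kinds of safety outcome: related adverse events, perioperative complications, and "device malfunctions, device removals, and hospital readmissions experienced by subjects post-LINX implant out to 12 months". SAP 1.2 carries the last four over as "perioperative complications, device malfunctions, device removals, and hospital readmissions experienced by subjects post-LINX implant out to 12 months". In both places the restriction to device or procedure relatedness attaches to the adverse events only.

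The visit schedule in Protocol 7.0 has one event row in Table 1, "Device and/or Procedure Adverse Events". In Table 3 the only event item at 2 weeks and at 3, 6 and 12 months is "device and/or procedure related adverse events". Table 1 also marks "Medical History" at baseline and 12 months, but the 12-month row of Table 3 has no history item.

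The documents then differ on which adverse events are recorded:

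- Protocol 11.9: "a reportable event will be defined as any untoward medical occurrence which has a strong relationship to the LINX device and/or implant procedure", with the further condition that another cause is unlikely. Protocol 12.1 asks the investigator to document reportable events.
- Protocol synopsis: safety rests on reporting every adverse event, and on the rate of serious related ones.
- SAP 8.6: "Safety will be assessed by the rate of AEs and SAEs (number and percentage of subjects experiencing", with related events summarised after that. Events graded Possibly or Unknown count as related. SAP Table 20 has a row for any adverse event, separate from the related rows.

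The SAP Appendix says that "a list of all listings to be created is provided corresponding to the eCRFs that are used during this study". None of the 23 listing titles names readmissions or malfunctions.

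**The concern.** The study is meant to support a label statement that LINX has been evaluated after sleeve gastrectomy, and Protocol 4.0 describes it as the first prospective study of the device in these patients. That is where attribution of an event to the device is least certain. If attribution decides whether an event is recorded at all, the readmission count depends on site judgement that nobody can later re-examine. A malfunction without harm may leave no record. A low or zero count could then be read as reassurance when it partly reflects what was asked.

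Follow-up contacts may also be made by telephone, apart from the tests that need a visit. An admission to another hospital could go unmentioned without a direct question.

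**Working it through.** **1. Does each named outcome have a visible route from collection to analysis?**

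| Outcome (Protocol 5.1) | Collection visible | Analysis visible |
|---|---|---|
| Related adverse events | Tables 1 and 3, every contact from implant on | Protocol 10.2; SAP 8.6, Table 20 |
| Perioperative complications | Table 3, implant row | SAP 8.4, Table 10 |
| Device removals | Explant box on the adverse event form, or withdrawal form | SAP explant programming note before Table 29 |
| Device malfunctions | No dedicated item | Not in Protocol 10.2 or SAP 8.6 |
| Hospital readmissions | No dedicated item | Not in Protocol 10.2 or SAP 8.6 |

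**2. What happens to specific events under each rule?**

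- *Readmission judged unrelated.* Not reportable under Protocol 11.9. Under the synopsis, and in the any-event row of SAP Table 20, it would count.
- *Readmission of uncertain cause.* Not reportable under 11.9, because the relationship is not strong. Under SAP 8.6 it would be graded Possibly or Unknown and counted as related. The SAP therefore analyses as related some events that the protocol does not require sites to report.
- *Malfunction without harm.* Not an untoward medical occurrence, so outside 11.9. Wider adverse event capture would not bring it in either.
- *Related readmission of 24 hours or less.* Reportable, but not serious on the hospitalization criterion alone, which requires more than 24 hours. The count of serious events therefore cannot stand in for a count of readmissions.

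**3. How large could the effect be?**

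There is no plan figure to reproduce: SAP 7 states that no sample size calculation was made, and neither document gives an expected readmission or malfunction rate. The following rests on assumptions. Take n = 30 (the planned maximum), all followed to 12 months, an all-cause readmission rate r, and a share s of readmissions that meet the 11.9 rule.

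Expected readmitted = 30r. Expected recorded = 30rs. Chance that none is recorded = (1 − rs)^30.

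| r | s | Readmitted | Recorded | Chance none recorded |
|---|---|---|---|---|
| 5% | 25% | 1.5 | 0.4 | 0.9875^30 = 69% |
| 10% | 50% | 3.0 | 1.5 | 0.95^30 = 21% |
| 20% | 75% | 6.0 | 4.5 | 0.85^30 = 0.8% |

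In the middle row, recording every readmission (s = 100%) would lower the chance of a zero count to 0.90^30 = 4.2%.

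Exact Clopper-Pearson 95% intervals at n = 30:

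- 3/30 = 10.0% (2.1% to 26.5%)
- 1/30 = 3.3% (0.1% to 17.2%)
- 0/30: upper limit 1 − 0.025^(1/30) = 11.6%

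The first two show how the picture would change if three subjects were readmitted and one admission met the rule. Those counts are an assumed example, not a trial estimate. The third applies to any zero count, and is valid only if the event was looked for in all 30 subjects.

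**The case against.** A reader might infer that the case report forms take only related events, so that readmissions are certainly under-counted and harmless malfunctions are zero by construction. The documents do not support that.

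- The forms (Protocol Appendix D) are not in the available text. The SAP's any-event row and its relatedness grades imply that the adverse event form can hold unrelated events.
- Listing titles are weak evidence. Explants have no listing of their own, yet they are captured by a box on the adverse event form or through the withdrawal form. The visit assessment, discharge, X-ray or unscheduled-visit forms may hold relevant fields.
- The table shells between Table 21 and the explant note before Table 29 are not in the available text, so it cannot be said that no table reports these outcomes.
- Neither document says that readmission means all-cause.
- Migration and erosion, if classed as malfunctions, are sought in all subjects by X-ray and endoscopy at 12 months.
- The 12-month history item in Table 1 may mean GERD history only.

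All of this stands, and it limits the conclusion to what may be missed. It does not close the gap. A form that can hold unrelated events is not an instruction to enter them, and 11.9 and 12.1 tell sites that they need not. The X-ray shell (SAP Table 16) asks about position and migration, not device integrity. SAP 4 says only that unscheduled-visit data will be listed.

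**Conclusion.** The point holds in a limited form. Two of the five named safety outcomes are undefined, have no visible schedule item or dedicated listing, and are absent from the sections that set out the safety analysis. The protocol's strong-relationship rule conflicts with the synopsis and with the SAP on which adverse events are recorded. A site following the protocol may leave out unrelated or uncertain readmissions and malfunctions without harm, so both **may** be under-counted. Whether they **are** depends on the forms, on what sites did, and on readmission meaning all-cause. It would go too far to call either outcome impossible to count.

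The size is unknown. Under the assumed ranges, the loss runs from about 1 of 1.5 expected readmitted subjects (1.5 − 0.4 = 1.1) to 1.5 of 6.0 (6.0 − 4.5). Those figures assume 30 subjects followed throughout. SAP 8.8 reports lower follow-up than anticipated, so the informative denominator may be smaller and the upper limit for a zero count above 11.6%.

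**What to change.** 1. Reconcile the adverse event scope across the synopsis, Protocol 11.9 and SAP 8.6, so that relatedness is a recorded attribute of an event and not a condition for recording it.
2. Define both outcomes, with readmission as all-cause. Unless the forms already do so, add two yes/no items at each existing follow-up contact (2 weeks, 3, 6 and 12 months): any hospital admission since the last contact, with date, reason and length; and any device malfunction, with or without harm.
3. In SAP 8.6, report the number and percentage of subjects with each outcome, an exact 95% confidence interval, and relatedness as a column.
4. Align Tables 1 and 3 on the 12-month history item and say what it covers.
5. The SAP is for the final analysis, and SAP 8.8 says that the initial enrolment of 30 is complete, so new questions cannot recover past visits. For those, query site records. Failing that, state in the report that these outcomes were not systematically sought, so that a low or zero count is not read as evidence of safety.

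The cost is two questions at existing contacts, one short form page and two table rows, plus site queries for completed visits. The readmission figure may turn out less favourable.
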